15.3.1 Events not reported as SAEs/SARs

The following events will not be classified as SAEs

Hospitalisation for:

- Routine treatment or monitoring of the studied indication not associated with any deterioration in condition.
- Treatment, which was elective or pre-planned, for a pre-existing condition, not associated with any deterioration in condition e.g. pre-planned hip replacement operation, which does not lead to further complications.
- Treatment on an emergency, outpatient basis for an event **not** fulfilling any of the definitions of serious as given above and not resulting in hospital admission.

15.4 RECORDING AND REPORTING AEs, ARs, SAEs, SARs AND SUSARs

Monitoring for safety events should commence on the date of consent and continue until a minimum of 30 days post last dose of randomised treatment.

AEs and SAEs will be collected on the relevant eCRF and reported to CTRU from the date of consent and continue until a minimum of 30 days post last dose of randomised treatment.

Reporting of ARs, SARs and SUSARs to CTRU should commence on the date of the first IMP dose taken and continue until a minimum of 30 days post last dose of randomised treatment.

15.4.1 SAEs AND SARs

All SAEs, SARs and SUSARs must be recorded on the SAE eCRF (in the case of SAEs and SARs) or SUSAR eCRF as appropriate and sent by secure file transfer to the CTRU via secure file transfer **within 24 hours** of the research staff becoming aware of the event.

Assessment of causality and expectedness must be made by an authorised physician. If an authorised physician is unavailable, initial reports without causality and expectedness assessment should be submitted to CTRU but must be followed up by medical assessment as soon as possible thereafter.

The original SAE/SUSAR Report CRF(s) should be retained by site until the event has reached a final outcome and all queries have been resolved (as determined by CTRU). When requested, please return original (wet-ink) initial and follow-up reports to CTRU and retain copies at site.

Each SAE will be described by:

- full details in medical terms and case description
- event duration (start and end dates, if applicable)
- action taken
- outcome
- seriousness criteria
- causality (i.e. relatedness to trial drug or PMR) in the opinion of the investigator
- whether the event would be considered expected or unexpected

Changes in outcome, seriousness criteria, causality, or significant / medically relevant changes to the event (key data) should be sent by secure file transfer to CTRU within 24 hours of becoming aware. Other follow up information should be sent by secure file transfer to CTRU when the event has reached a final outcome, or when requested. Events will be followed up until the event has resolved or a final outcome has been reached.

[figure not shown]
Please ensure that each SAE/SAR/SUSAR event is reported separately and not combined on one form.

Investigators must report all SAEs to their host institution in line with their local arrangements.

15.4.2 SUSARs

All SAEs assigned by the PI or delegate (or following central review) as both suspected to be related to IMP-treatment and unexpected will be classified as SUSARs and will be subject to expedited reporting to the Medicines and Healthcare products Regulatory Authority (MHRA). The CTRU will inform the MHRA, the main REC and the Sponsor of SUSARs within the required expedited reporting timescales.

15.5 OVERVIEW OF THE SAFETY REPORTING PROCESSES

Pregnancies
Site staff should notify the CTRU of a pregnancy in a trial subject or the partner of a trial subject and the estimated due date immediately on the Notification of Pregnancy CRF.

** The following events should also be regarded as SAEs in participants receiving **abatacept**:
1) Cancer 2) Overdose leading to an SAE 3) Pregnancy 4) Medication error leading to an SAE 5) Suspected transmission of an infectious agent via the drug 6) Potential Drug Induced Liver Injury (DILI).

*The Chief Investigator (or delegate) will review all received SUSARs for seriousness, expectedness and causality. All SUSARs or increase in trends or severity of SARs will be identified and expeditiously reported to the MREC, MHRA and Sponsor.

15.6 PREGNANCY

Pregnancy in participants participating in this study must be prevented as effectively as possible. Pregnancies and suspected pregnancies (including a positive pregnancy test regardless of age or disease status) in a participant occurring during the trial must be recorded on the Notification of Pregnancy Form and sent by secure file transfer to the CTRU **within 24 hours** of the research staff becoming aware of the event.

Pregnant participants must be followed until the end of their pregnancy and the CTRU must be notified of the outcome of the pregnancy (including false-positive pregnancy tests) within 24 hours of this information being known. If a pregnancy occurs in a male participant's partner, details of the pregnancy will still be collected where possible and the outcome of the pregnancy must be notified to CTRU.

The outcome of any pregnancy which qualifies as a SAE (i.e. spontaneous or therapeutic abortion, foetal and neonatal death, or congenital abnormalities – including those detected in an aborted foetus), birth defects, or the death of an infant which occurs in connection with in utero exposure to the study drugs must be reported to the CTRU as a SAE in accordance with Section 15.4.1

All DMARD treatment must be stopped immediately if a pregnancy in a female participant occurs or is suspected. Relevant clinical guidelines should be followed. At the time of writing this includes the 2022 British Society for Rheumatology guidelines (53) and the 2020 American College of Rheumatology guidelines (54); for MTX it is advised to stop MTX and commence folic acid 5mg daily whereas for LEF cholestyramine washout and measurement of post-washout LEF levels is advised.

Participants withdrawn from treatment will still attend for follow-up assessments unless unwilling to do so and case report forms will continue to be collected. Pregnant female participants should be referred to an obstetrician/gynaecologist experienced in reproductive toxicity for further evaluation and counselling. The pregnancy will be followed up until final outcome (termination of pregnancy, miscarriage, stillbirth or live birth).

15.6 RESPONSIBILITIES

Principal Investigator (or delegate) at site:

- Checking for AEs/SAEs during telephone follow-up assessments
- Checking for AEs/SAEs when participants attend for treatment / follow up.
- Using medical judgement in assigning seriousness, causality and expectedness using the Reference Safety Information approved for the trial.
- To ensure all SAEs and SARs (including SUSARs) are recorded and reported to the CTRU within 24 hours of becoming aware of the event and to provide further follow up information as soon as available. Ensuring that SAEs and SARs (including SUSARs) are chased with CTRU if a record of receipt is not received within 2 working days of initial reporting.
- Ensuring that AEs and ARs are recorded and reported to the CTRU in line with the requirements of the protocol.

- Communication to the GP of any clinically relevant change in the participant's medical condition that might affect their ongoing care, including management of co-morbidities.

Chief Investigator (or nominated individual in CI's absence):

- Clinical oversight of the safety of trial participants, including an ongoing review of the risk / benefit.
- Using medical judgment in assigning seriousness, causality and expectedness of SAEs where it has not been possible to obtain local medical assessment.
- Immediate review of all SUSARs.
- Review of specific SAEs and SARs in accordance with the trial risk assessment and protocol as detailed in the Trial Monitoring Plan.
- Assigning Medical Dictionary for Regulatory Activities (MedDRA) or Body System coding to all SAEs and SARs.
- Preparing the clinical sections and final sign-off of the Development Safety Update Report (DSUR).

CTRU:

- Central data collection and verification of AEs, ARs, SAEs, SARs and SUSARs according to the trial protocol onto a MACRO database.
- Reporting safety information to the CI, delegate or independent clinical reviewer for the ongoing assessment of the risk / benefit according to the Trial Monitoring Plan.
- Reporting safety information to the independent oversight committees identified for the trial (Data Monitoring & Ethics Committee (DMEC) and / or Trial Steering Committee (TSC)) according to the Trial Monitoring Plan.
- Expedited reporting of SUSARs to the Competent Authority (MHRA in UK), main REC and Sponsor within required timelines.
- Notifying Investigators of SUSARs that occur within the trial.
- Reporting events to collaborating pharmaceutical company in accordance with the trial contract.
- Checking for (annually) and notifying PIs of updates to the Reference Safety Information for the trial.
- Preparing standard tables and other relevant information for the DSUR in collaboration with the CI and ensuring timely submission to the MHRA and Main REC.

TSC:

- In accordance with the Trial Terms of Reference for the TSC, periodically reviewing safety data and liaising with the DMEC regarding safety issues.

DMEC:

- In accordance with the Trial Terms of Reference for the DMEC, periodically reviewing unblinded overall safety data to determine patterns and trends of events, or to identify safety issues, which would not be apparent on an individual case basis.

16 OUTCOME MEASURES

16.1 PRIMARY OUTCOME MEASURE

The primary outcome measure is mean participant reported cumulative prednisolone dose between randomisation and 18 months post-randomisation, reported by participants via a monthly questionnaire.

Where a participant receives an alternative steroid medication to prednisolone, the steroid dose will be converted to a “Prednisolone equivalent dose” prior to analysis.

Intercurrent events of interest are:

- Death – to be handled under a treatment policy strategy;
- Discontinuation of trial treatment (including crossover to other arm) – to be handled under a treatment policy strategy;

Although steroid diaries are a part of routine clinical care, we acknowledge a lack of data as to the accuracy of participant-completed steroid diaries as a means to track medication usage. We have identified only small-scale results, incompletely reported and for different populations, claiming that medication diaries have satisfactory test-retest reliability (62) and that comparable methods of medication use surveillance lead to similar reported adherence levels (63).

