17. STATISTICAL CONSIDERATIONS

Sample size

In UK primary care (Clinical Practice Research Datalink), patients with relapsing PMR had a mean cumulative prednisolone dose of 5g over 18 months (coefficient of variation (CV) 0.78) (68).

A clinically relevant reduction is benchmarked against the reduction likely to substantively reduce the risk of fracture or infection. Extrapolating from observational data, an average reduction in cumulative prednisolone dose of 1.5g (a reduction in mean daily dose of 2.7mg over 18 months) would be predicted to significantly reduce hip and vertebral fracture risk (69). This corresponds to a 30% reduction in cumulative dose. Our PPI group helped inform this target effect size: discussions around trade-offs revealed that most would not consider a DMARD worth it unless it could substitute for more than 2.5mg daily prednisolone over an 18-month period.

Assuming a log-normal distribution, 200 participants will provide 90% power to detect a target 30% reduction in cumulative prednisolone dose, assuming a CV of 0.78, 2-sided independent t-test for fold change (H0: mean fold change=1), 5% significance and 20% attrition (24) (nQuery v3.0). The trial will retain at least 80% power if the CV is as large as 0.94.

As part of this Australia is recruiting 50 participants there for 25% of the total number for the study.

Planned recruitment rate

Recruitment from secondary care: there will be 3 sites. Each site is expected to be open and recruiting participants over a 12-month period.

We estimate a 3:1 screen: recruitment ratio as being realistic. From the PCRN route plus referrals from rheumatologists, GPs and self- referrals, it is estimated that 150 participants will attend screening visits and 50 will be randomised in Australia.

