18. STATISTICAL ANALYSIS

18.1 GENERAL CONSIDERATIONS

A full statistical analysis plan (SAP) will be in place prior to any comparative analyses according to guidelines (70) The statistical analysis is the responsibility of the CTRU Statistician and will not include the economic evaluation (section 16). All analyses and patient populations will be predefined in the SAP.

The intention to treat (ITT) population will include all randomised patients, to be analysed in groups assigned at randomisation. A per-protocol population will be defined accounting for major protocol deviations, relating to intervention compliance, eligibility and other criteria agreed by the Trial Management Group prior to any unblinded efficacy analyses. Participants in the Per-Protocol population will be analysed according to randomised allocation.

Primary analysis will be conducted on the intention-to-treat (ITT) population; a secondary per-protocol population analysis will also be undertaken. Statistical monitoring of safety data and underlying assumptions of the statistical design will be conducted and reported to the Data Monitoring and Ethics Committee (DMEC) according to an agreed DMEC Charter.

At the time of the final analysis, the trial will be analysed and reported according to the CONSORT reporting standards (71).

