18.2 ANALYSIS OF PRIMARY OUTCOME MEASURE

The primary analysis on log (cumulative prednisolone-equivalent dose reported over 18 months) will use multivariable linear regression, with covariates for the minimisation factors (listed in Section 11.3); age at randomisation will be retained as a continuous covariate, under transformation as necessary. Adjusted mean fold difference in cumulative prednisolone dose will be presented with 95% confidence interval (CI) and significance. Summaries on mean fold difference and absolute difference in cumulative prednisolone dose will be presented.

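### Treatment policy cannot be applied to death for an 18-month dose total, and its natural reading gives participants who die favourable values

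*Protocol*

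**What the plan says.** Section 16.1 defines the primary outcome as "mean participant reported cumulative prednisolone dose between randomisation and 18 months post-randomisation". It lists two intercurrent events and gives both the same strategy. For death the entry is "Death – to be handled under a treatment policy strategy"; the other entry covers discontinuation of trial treatment, including crossover.

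Section 18.2 fixes the model: "The primary analysis on log (cumulative prednisolone-equivalent dose reported over 18 months) will use multivariable linear regression". The covariates are the minimisation factors and age, with no term for time alive. The population in section 18.1 is everyone randomised: "The intention to treat (ITT) population will include all randomised patients, to be analysed in groups assigned at randomisation". People who die are therefore in the primary comparison.

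No section says how the total is formed after a death. Section 14.10 interpolates between questionnaires where needed. Section 18.5 allows imputation of missing outcomes and promises sensitivity analyses, but does not mention death.

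Other outcomes do deal with death. In section 16.2.2, time to steroid cessation is censored at death, and the relapse count uses a time at risk that ends at death, which enters the model in section 18.3 as an offset. Section 18.3 summarises deaths by treatment received.

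**The concern.** Treatment policy works for stopping the DMARD or crossing over, because the participant goes on taking, or not taking, steroid and that dose can be recorded. It does not work for death. The 18-month total either does not exist or has to be taken as the sum so far.

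If the sum so far is used, a death in the second month produces one of the lowest totals in the trial, and a lower total counts as better. The log scale enlarges this, because a small fraction of a usual total becomes a large negative shift.

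The primary estimate would then partly measure mortality. Excess deaths in the DMARD arm would look like steroid sparing, and excess deaths under usual care would hide it. Some deaths are plausible: section 5.1 puts average onset at around 75 years, and the background says that older and frailer patients are deliberately included.

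**Working it through.** **1. The plan's own figure.** Section 17 states that "200 participants will provide 90% power to detect a target 30% reduction in cumulative prednisolone dose". The inputs it gives are a log-normal outcome with CV 0.78, a two-sided t-test at the 5% level and an attrition allowance of 20%.
- Log-SD = sqrt(ln(1 + 0.78²)) = sqrt(0.4752) = 0.689.
- Target effect = |ln 0.70| = 0.357.
- The noncentral t needs 80 per arm, and 80/0.80 = 100 per arm, so 200 in total. Power at 80 per arm is 90.2%.
- At CV 0.94 the log-SD is sqrt(ln(1 + 0.94²)) = 0.796 and power is 80.4%, matching the stated tolerance.

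The sample size reproduces.

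**2. Effect of one death, if the sum to death is used.** With a constant dose, death after a fraction u of follow-up shifts the log total by ln(u). Over 80 weeks:

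| Death at week | Log shift | Shift in arm mean (1 of 80), as share of 0.357 |
|---|---|---|
| 4 | -3.00 | 10.5% |
| 20 | -1.39 | 4.9% |
| 40 | -0.69 | 2.4% |
| 60 | -0.29 | 1.0% |

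As a second dose profile, assume purely for illustration a linear fall from 14 to 4 mg. Its mean is 9 mg per day, or about 4.9 g over 18 months, close to the 5 g in section 17. The shift is then ln((14u - 5u²)/9). A death at week 8 (u = 0.1) shifts the log total by -2.30 (constant) or -1.90 (falling), which is 3.3 or 2.8 log-SDs.

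**3. Unbalanced deaths, no drug effect.** Assume deaths uniform over follow-up. The mean shift is -1.00 (constant) or -0.763 (falling). With 6% v 2% deaths the log contrast moves by 0.04 × 1.00 = 0.040 or 0.04 × 0.763 = 0.031. The spurious fold is exp(-0.040) = 0.961 or exp(-0.031) = 0.970. The standard error is 0.689 × sqrt(2/80) = 0.109, so the shift is 0.28 to 0.37 of a standard error.

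**4. Direction.** A separate simulation took deaths as uniform from week 4 to week 80, a true fold of 0.70, and a constant dose or a linear taper to zero. Deaths of 3% under usual care and 8% under DMARD gave a fold of 0.671 to 0.684. The reverse gave 0.717 to 0.730.

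**5. Balanced deaths, 5% per arm.** Variance = 0.4752 + p·E[X²] - p²·E[X]², where X is the shift.
- Constant dose: 0.4752 + 0.05 × 2 - 0.0025 × 1 = 0.5727, SD 0.757.
- Falling dose: 0.4752 + 0.05 × 1.384 - 0.0025 × 0.582 = 0.5430, SD 0.737.
- Power at 80 per arm: 84% and 86%.
- If the 20% attrition was meant to include deaths, analysing them gives about 85 per arm, and power at the same SDs is 86% and 88%.

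Both SDs are below 0.796.

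**The case against.** A reader might infer that the protocol scores post-death dose as zero, so that every death counts as steroid saving. It does not say so. Section 18.5 leaves room for imputation, section 18.1 defers the detail to an SAP that is not shown, and the sum to death is only the natural reading of a label that cannot be applied. That objection stands against the strong reading. It does not rescue the rule: imputing a dose after death is a hypothetical strategy and contradicts section 16.1. An SAP must therefore either keep the fault or depart from the protocol on the primary estimand.

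A reader might also infer that deaths leave the trial underpowered. They do not, at the rates considered. Section 17 already allows for a CV of 0.94, the SDs above stay inside it, covariate adjustment may reduce the residual SD, and the data monitoring committee reviews the variability of the primary outcome (section 18.6).

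Nor is there a built-in bias towards the DMARD. Equal deaths with equal timing leave the contrast unbiased, and excess deaths under usual care work against the DMARD. The mortality rates and the imbalance are assumed, and the resulting bias is small beside a fold of 0.70.

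**Conclusion.** The point holds as a fault in the stated estimand. Section 16.1 assigns death to a strategy that cannot be carried out for a dose total to 18 months. Its natural reading treats early death as a favourable result, while section 16.2.2 handles death explicitly for other outcomes. This is a rule stated wrongly, not a detail left to the SAP.

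The likely numerical effect is modest: a spurious fold of about 0.96 to 0.97 at 6% v 2% deaths, and power of about 84 to 88% in place of 90% at 5% per arm. Both figures assume uniform timing of death and that the sum to death is what gets analysed. Individual early deaths weigh most.

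Severity: should-fix, on the ground of what the estimate means rather than its power.

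**What to change.** In section 16.1, for death only, replace treatment policy with one workable strategy fixed before any comparative analysis. Keep treatment policy for discontinuation and crossover. Two options are defensible:

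- **While-alive:** analyse the log of mean daily dose over time alive, in line with the time-at-risk approach used for relapses. For participants followed to 18 months, this divides the total by a fixed number of days and leaves the log contrast unchanged.
- **Hypothetical, labelled as such:** complete the total by imputing the doses that would have been taken. The text should not also describe the post-death months as non-existent, because that is a different estimand.

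Add a sensitivity analysis that treats death as unfavourable, and show deaths by randomised arm beside the primary result.

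The cost is one sentence in section 16.1, matching SAP wording and one extra analysis; N does not change. Either option changes the estimand for the few who die, which is why the sensitivity analysis is needed. While-alive is not neutral when dose is falling: in the 14 to 4 mg illustration, a death at week 8 has a mean daily dose of 14 - 5 × 0.1 = 13.5 mg against 9 mg, a log shift of +0.41. That is much smaller than the -1.90 on the total, and it no longer rewards death.

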16.2 SECONDARY OUTCOME MEASURES

16.2.1 Participant reported outcomes

16.2.1.1 PMR Symptom Severity – Mean PMR-IS Symptom domain score, Mean PMR-IS Symptom function score, Mean PMR-IS Psychological/Emotional well-being domain score, Mean PMR-IS Steroid side effect domain score – all at each of the timepoints [Weeks 12, 24, 36, 48, 60, 72, 80 post randomisation]

PMR-Impact Scale (PMR-IS) comprises four domains: symptoms, function, psychological and emotional well-being, and steroid side effects (64, 65). Scores are presented separately for each domain to aid clinical utility. In each domain, the domain score is derived as the mean of the item responses, converted to a percentage (0-100) with higher scores representing better status domain.

None of the domains of the PMR-IS has been identified as being of a priori importance.

16.2.1.2 Health-related Quality of Life – Mean EQ-5D-5L Utility [Weeks 12, 24, 36, 48, 60, 72, 80 post randomisation]

The five categorical domain responses to the EQ-5D-5L will be converted to a utility score, following the value set approved by NICE.

At time of protocol v1.0, the approved mapping of responses to utilities is following the Crosswalk algorithm of van Hout et al (66). Should NICE approve an alternative value set, this will be used instead.

16.2.1.3 PMR Disease Activity (Mean PMR Activity Score (PMR-AS) at weeks 4, 24 and 80)

The PMR-AS (ref) is a composite measure, derived from the following clinical and participant-reported measures:

- * C-reactive protein (CRP, mg/dL)
- * Participant-reported pain, assessed on a visual analogy scale (VASp, range 0 to 10)
- * Duration of morning stiffness (MS; in minutes)
- * Upper limb elevation (active shoulder abduction, ULE range 0 to 3)
- * Physician disease activity assessed on a VAS (VASph, range 0 to 10).

The derivation is $PMR-AS = CRP + VASp + (MS \times 0.1) + ULE + VASph$.

